7 DOSING DELAYS/DOSE MODIFICATIONS

General guidelines for treatment modifications at the time of re-treatment:

Adverse Events: All adverse events in this trial will be graded using the NCI Common Terminology Criteria for Adverse Events (CTCAE) version 5.0. A complete listing is available at the CTEP website: <http://ctep.cancer.gov/forms/CTCAEv5.pdf>.

7.1 Birinapant

7.1.1 Safety Consideration When Administering Birinapant

7.1.2 Dose Adjustments

Dose adjustments are allowed during both the dose escalation and the expansion phase of the study. Patients that have a DLT as defined in Section 6.2 may have their treatment held or will

incur up to 2 dose level reductions, as indicated in Section 7.1.3. If an AE that fulfills DLT criteria recurs, treatment will be held as noted below and resumed at 1 dose level lower. If a third AE fulfilling DLT criteria occurs, treatment with birinapant will be permanently discontinued, but IMRRT may be continued, provided in-field radiation toxicity is not limiting. Patients that are retreated at a lower dose level than initially assigned will not be included in the assessment of DLTs for that lower dose level (with the exception of level -1 dose) but will be included in the analysis of secondary endpoints.

In case of grade 4 non-hematologic toxicity or any grade 3 toxicity not returning to \leq grade 1 after 2 weeks of supportive care, patients will be taken off birinapant treatment and may continue with IMRRT only. Patients who experience a DLT related to the combination at a specific dose level will have both their treatments held (both birinapant and IMRRT) for up to 2 weeks and supportive measures will be implemented to ameliorate the AE. Once the AE is \leq grade 1, treatment with birinapant will be resumed at 1 dose level lower. In case of concurrent elevation of AST/ALT $>$ 3 times the upper limit of normal and bilirubin $>$ 2 times the upper limit of normal (i.e., Hy's law), study treatment will be permanently discontinued.

Dose adjustments are allowed during the expansion part of the study according to the guidelines below, with dose levels defined as follows:

Dose Level	Birinapant (mg/m ²)
-1	2.8
1	5.6
2	11
3	17
4	24

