6.5 Duration of Therapy

In the absence of treatment delays due to adverse event(s), treatment may continue for 2 cycles or until one of the following criteria applies:

- Disease progression
- Intercurrent illness that prevents further administration of treatment
- Unacceptable adverse event(s) as described in Sections [6.2](#) and [7](#).
- Patient decides to withdraw from the study
- General or specific changes in the patient's condition that render the patient unacceptable for further treatment in the judgment of the investigator

- Clinical progression
- Patient experiences a grade 4 non-hematologic toxicity or any grade 3 toxicity not returning to \leq grade 1 after 2 weeks of supportive care. The patient may continue with IMRRT but will be taken off birinapant.
- Patient non-compliance with <80% of birinapant doses (less than 3 out of the 4 total doses) or with scheduled appointments for investigational treatment that may affect treatment outcome, per PI discretion.
- Pregnancy
 - All women of child bearing potential will be instructed to contact the investigator immediately if they suspect they might be pregnant (e.g., missed or late menstrual period) at any time during study participation.
 - The investigator must immediately notify CTEP in the event of a confirmed pregnancy in a patient participating in the study.
- Termination of the study by sponsor
- The drug manufacturer can no longer provide the study agent

The reason(s) for protocol therapy discontinuation, the reason(s) for study removal, and the corresponding dates must be documented in the Case Report Form (CRF).

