7.2 Radiation treatment

In the event of febrile neutropenia or severe radiation related toxicity (grade 4), that in the judgement of the PI or local PI would contraindicate continuing radiation, radiation treatment

may be held temporarily. Similarly, medical events that require hospitalization or would interfere with patient setup, alignment, or delivery of radiation may also result in a temporary treatment break. If a patient requires a cumulative treatment break for 10 business days (2 weeks) they will be removed from protocol therapy.

If IMRRT is held temporarily, birinapant will be held too and restarted with IMRRT.

If IMRT is discontinued, birinapant will be stopped and patient will be taken off study treatment.

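### The grade 4 row for birinapant-related anemia is weaker than the grade 3 row and conflicts with 7.1.2; a lesser conflict between 7.1.2 and 7.2 arises when IMRRT breaks total 10 business days

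*Combined protocol and SAP*

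**What the plan says.** **Grade 4 anemia.** Under 6.2, hematologic toxicity of grade 4 or worse is a DLT if it is possibly attributable to the combination and falls within 42 days of the start of therapy. Lymphopenia is the only exception.

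Section 7.1.2 gives two instructions for a patient with a DLT:
- The first paragraph says the patient may have treatment held or will "incur up to 2 dose level reductions, as indicated in Section 7.1.3".
- The second paragraph says that patients with a combination-related DLT "will have both their treatments held (both birinapant and IMRRT) for up to 2 weeks", and that once the event is grade 1 or less, "treatment with birinapant will be resumed at 1 dose level lower".

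Section 7.1.3.3, which by its title covers anemia related to birinapant, requires at grade 3 a hold, a restart one level lower, and a permanent stop of birinapant at the third occurrence. At grade 4 it asks for transfusion and supportive therapy, and leaves continuation to the investigator in light of attribution.

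**Treatment breaks.** If a DLT-type event recurs, 7.1.2 says "treatment will be held as noted below and resumed at 1 dose level lower". For grade 3 toxicity not resolved after 2 weeks of supportive care, it says "patients will be taken off birinapant treatment and may continue with IMRRT only". Section 6.5 says of the same situation: "The patient may continue with IMRRT but will be taken off birinapant". Section 7.2 says: "If a patient requires a cumulative treatment break for 10 business days (2 weeks) they will be removed from protocol therapy". It states no exemption for DLT holds.

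**The concern.** The anemia table is less strict at the worse grade. Grade 3 anemia, which is not by itself a DLT, triggers a mandatory hold and reduction; grade 4 anemia, which is a DLT, triggers neither in its own row. A site that treats the specific table row as governing could re-dose at the same level after a DLT. A site that follows the second paragraph of 7.1.2 would hold both treatments and reduce.

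On breaks, the two-week hold in 7.1.2 and the removal limit in 7.2 fall at the same point but lead to different actions. A patient who has recovered from a DLT when IMRRT breaks reach that total could be re-dosed at one site and removed at another, with each site following a section of the protocol. What is at stake in both points is patient safety and uniform handling across sites.

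**Working it through.** **Part 1: the three hematologic tables side by side.** No arithmetic applies.

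| Table | Grade 3 | Grade 4 |
|---|---|---|
| 7.1.3.1 Neutropenia | Hold, one level lower; stop at third occurrence | Hold, one level lower; stop at third occurrence |
| 7.1.3.2 Thrombocytopenia | Hold, one level lower; stop at third occurrence | Hold, one level lower; stop at third occurrence |
| 7.1.3.3 Anemia | Hold, one level lower; stop at third occurrence | Transfuse and support; continuation at discretion |

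One of three tables lacks a mandatory grade 4 hold and reduction. The conflict with 7.1.2 then follows in steps:
1. The anemia table covers only birinapant-related events, so attribution to birinapant is already settled when the grade 4 row is reached. Its attribution test adds nothing within that scope.
2. Such an event at grade 4 is at least possibly attributable to the combination, so within 42 days it is a DLT under 6.2.
3. The second paragraph of 7.1.2 then requires a hold of both treatments and a one-level reduction.
4. The row requires neither, yet the first paragraph of 7.1.2 sends the reader to 7.1.3 for the reductions.

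**Part 2: the 10-business-day limit.** The inputs are the hold of up to 2 weeks (7.1.2), the removal point of 10 business days (7.2), and radiation Monday to Friday (section 6). The method is to count Monday-to-Friday days in a hold of n calendar days for each of the 7 possible start days, ignoring holidays.

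- The plan's own equation of 10 business days with 2 weeks reproduces: 14 days = 2 × 7, giving 2 × 5 = 10 weekdays from every start day.
- 13 days: 9 or 10.
- 12 days: 8 to 10, with 10 only from a Monday start.
- 11 days: 7 to 9, so the limit is never reached by a single hold of this length.
- 7 days: 5 from every start day, so two one-week holds give 5 + 5 = 10.
- Two maximum holds: 10 + 10 = 20, twice the 7.2 limit.
- The hematologic tables stop birinapant at a delay of 16 or more consecutive days. A 15-day hold already contains 10 or 11 weekdays, so when IMRRT is also held, the 7.2 limit is reached first.

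Instructions once IMRRT breaks total 10 business days:

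| Patient | 7.1.2 and 6.5 | 7.2 |
|---|---|---|
| Recovered to grade 1 or less | 7.1.2: resume birinapant one level lower | Removed from protocol therapy |
| Grade 3, not recovered | Stop birinapant; IMRRT may continue | Removed from protocol therapy |

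The first row is a direct contradiction. The second is weaker, because continuing IMRRT is permitted and not required.

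**The case against.** **On anemia.** The strongest reply is that the second paragraph of 7.1.2 is mandatory and already covers a combination-related grade 4 anemia. This stands in large part. A reader might infer from the table alone that birinapant-related grade 4 anemia carries no required hold or reduction anywhere in the protocol; 7.1.2 shows otherwise. The reply does not remove the conflict, because the specific row says something different and 7.1.2 itself refers to 7.1.3. It can also be said that tying discretion to attribution comes close to limiting it to unrelated anemia. The row does not say that, and its table is confined to related events.

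**On breaks.** The two sections can be reconciled: recover within two weeks and resume, or reach the limit and come off. That is a sensible reading, but neither section states it, and a full two-week hold is allowed by one section and ends protocol therapy under the other. Three limits on this point stand:
- A reader might infer that 6.5 and 7.1.2 flatly contradict 7.2 for unresolved grade 3 toxicity. They do not: both only permit IMRRT to continue, so a site that removes the patient breaches neither. Where only birinapant was held, no IMRRT break accrues at all.
- Totals of 9 or fewer business days cause no conflict, and a public holiday could bring a 14-day hold down to 9.
- There are only four birinapant doses, so the resume-or-remove conflict needs a dose still to be given.

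**Conclusion.** The anemia row should be corrected. It is weaker at grade 4 than at grade 3, conflicts with the second paragraph of 7.1.2, and differs from the grade 4 rows of the other two hematologic tables. This rests on reading a birinapant-related event as related to the combination. With 7.1.2 as a partial safeguard, the defect is an inconsistent and weaker row.

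The break conflict is minor. It is firm for a recovered patient with doses remaining whose IMRRT holds total 10 business days, whether from one full hold or repeat holds such as 5 + 5. It assumes that IMRRT itself was held, that no holiday intervenes, and that the unqualified removal sentence in 7.2 covers DLT holds.

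The documents give no rate for grade 4 anemia or for breaks of this length, so the frequency of both is unknown. A reader might infer that dose-finding results are affected; nothing here changes an MTD, power or sample-size figure.

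**What to change.** 1. **7.1.3.3, grade 4 row.** For anemia attributed to birinapant, require at least the grade 3 hold and one-level reduction, with the same stop rules (third occurrence, delay of 16 or more consecutive days, more than two reductions). Keep investigator discretion only for anemia not attributed to birinapant.
2. **7.1.2 and 7.2.** State which rule governs once all IMRRT breaks, including DLT holds and mixed causes (for example 5 days for a DLT and 5 for hospitalization), total 10 business days. The simplest version is that resumption under 7.1.2 applies only before the 7.2 limit is reached. The same sentence should say whether IMRRT may still be completed on protocol after that point. Other single rules would also resolve the conflict; that is a clinical choice for the sponsor.

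The cost is a wording amendment to three sections and slightly less investigator discretion at grade 4 anemia. No visits, procedures or patients are added.

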7.1.3 Dose Modifications for Hematologic Toxicity

7.1.3.1 Dose Modification Guidelines for Birinapant-related Neutropenia

Event Name	Neutropenia
Grade of Event	Management/Next Dose for Birinapant
\leq Grade 1	No change in dose
Grade 2	Hold until \leq Grade 1. Resume at same dose level.
Grade 3	First occurrence: Hold * birinapant until return to \geq 1500/mm ³ ; restart therapy at 1 dose level lower. Use of cytokine growth factor (G-CSF or GM-CSF) supportive care may be implemented. Second occurrence: Hold * birinapant until return to \geq 1500/mm ³ ; restart therapy at 1 dose level lower **. Use of cytokine growth factor (G-CSF or GM-CSF)

	
supportive care may be implemented based on the judgment of the investigator for continued treatment.
 
Third occurrence: The study participant will not receive additional birinapant and will stop further birinapant but continue on study for follow up.

Grade 4	
First occurrence: Hold * birinapant until return to $\geq 1500/\text{mm}^3$; restart therapy at 1 dose level lower. Use of cytokine growth factor (G-CSF or GM-CSF) supportive care may be implemented based on the judgment of the investigator for continued treatment.
 
Second occurrence: Hold * until return to $\geq 1500/\text{mm}^3$; restart therapy at 1 dose level lower **. Use of cytokine growth factor (G-CSF or GM-CSF) supportive care may be implemented.
 
Third occurrence: The study participant will not receive additional birinapant and will stop further birinapant but continue on study for follow up as described in Section 6

	
*Participants requiring a delay of ≥ 16 consecutive days must stop birinapant
 
**Participants requiring $>$ two dose reductions must stop birinapant.

7.1.3.2 Dose Modification Guidelines for Birinapant-related Thrombocytopenia

Event Name	Thrombocytopenia
Grade of Event	Management/Next Dose for Birinapant
\leq Grade 1	No change in dose
Grade 2	Hold * birinapant until \leq Grade 1. Resume at same dose level.
Grade 3	
First occurrence: Hold * birinapant until return to $\geq 75,000/\text{mm}^3$; restart therapy at 1 dose level lower.
 
Second occurrence: Hold * birinapant until return to $\geq 75,000/\text{mm}^3$; restart therapy at 1 dose level lower **.
 
Third occurrence: The study participant will not receive additional birinapant and will stop further birinapant but continue on study for follow up as described in Section 6

Grade 4	First occurrence: Hold* birinapant until return to $\geq 75,000/\text{mm}^3$; restart birinapant at 1 dose level lower**.
	Second occurrence: Hold* birinapant until return to $\geq 75,000/\text{mm}^3$; restart therapy at 1 dose level lower**.
	Third occurrence: The study participant will not receive additional birinapant and will stop further birinapant but continue on study for follow up as described in Section 6
	*Participants requiring a delay of ≥ 16 consecutive days must stop birinapant
	**Participants requiring $>$ two dose reductions must stop birinapant.

7.1.3.3 Dose Modification Guidelines for Birinapant - related Anemia

Event Name	Anemia
Grade of Event	Management/Next Dose for Birinapant
\leq Grade 1	No change in dose
Grade 2	Hold* birinapant until return to $\text{Hgb} \geq 10 \text{ g/dL}^{**}$; transfusion is allowed to achieve $\text{Hgb} > 10 \text{ g/dL}^{***}$. No change in dose
Grade 3	First occurrence: Hold birinapant until return to $\text{Hgb} \geq 10 \text{ g/dL}^*$; transfusion is allowed to achieve $\text{Hgb} > 10 \text{ g/dL}^{***}$. Restart birinapant at 1 dose level lower.
	Second occurrence: Hold birinapant until return to $\text{Hgb} \geq 10 \text{ g/dL}^*$; transfusion is allowed to achieve $\text{Hgb} > 10 \text{ g/dL}^{***}$. Restart birinapant at 1 dose level lower****.
	Third occurrence: The study participant will not receive additional birinapant and will stop further birinapant but continue on study for follow up as described in Section 6
Grade 4	Transfuse and initiate appropriate supportive therapy. Continuation of birinapant is at the discretion of the Investigator depending on the attribution assigned to the anemia.
*Participants requiring a delay of ≥ 16 consecutive days must stop birinapant.	
**Transfusion is allowed to achieve $\text{Hgb} > 10 \text{ g/dL}$.	
*** Erythropoiesis stimulating agents are not allowed due to possible increased risk of inhibition of apoptosis pathway and disruption of NF κ B-mediated tumor cell killing.	
****Participants requiring $>$ two dose reductions must stop birinapant.	

7.1.4 Dose Modification Guidelines for Birinapant-related Non-hematologic Toxicities

Non-hematologic Toxicities	
Grade of Event	Dose Modification
Grade 1	Continue at same dose level.
Grade 2	Hold* dose until recovery to baseline or Grade \leq 1 with standard supportive therapy. Resume at current dose. For second hold for Grade 2, hold until recovery to grade 1 and restart at one dose level lower. If no recovery to grade 1 within 16 days, the study participant will not receive additional birinapant and will stop further birinapant administration but continue on study for follow up as described in Section 6
Grade 3	First occurrence: Discontinue further birinapant or withhold birinapant until recovery to baseline or Grade \leq 1 with standard supportive therapy. Birinapant will be restarted at 1 dose level lower. As an exception, grade 3 non-hematologic laboratory abnormalities without clinical symptoms that resolve to Grade 1 or baseline (if the study participant entered the study with existing toxicity) within 7 days will not lead to dose modification. Second occurrence: Discontinue further birinapant or withhold birinapant until recovery to baseline or Grade \leq 1 with standard supportive therapy. Therapy will be restarted at 1 dose level lower. Third occurrence: The study participant will not receive additional birinapant and will stop further birinapant but continue on study for follow up as described in Section 6.
Grade 4	The study participant will stop further birinapant but continue on study for follow up as described in Section 6. If a study participant experiences a grade 4 toxicity lasting less than 24 hours, re-initiation of birinapant at 1 dose level lower may be considered after recovery to baseline or Grade \leq 1 with standard supportive therapy.
*Participants requiring a delay of \geq 16 consecutive days must stop birinapant	
**Participants requiring $>$ two dose reductions must stop birinapant.	

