7.1.5.2 Management of Vomiting

Event Name	Vomiting
Grade of Event	Management/Next Dose for Birinapant
≤ Grade 1	No change in dose
Grade 2	Hold* until ≤ Grade 1. Resume at same dose level.
Grade 3	Hold* until < Grade 1. Resume at same dose level.**
Grade 4	The study participant will stop further birinapant but continue on study for follow up as described in Section 6. If a study participant experiences grade 4 vomiting lasting less than 24 hours, reinitiation of birinapant at 1 dose level lower may be considered after recovery to baseline or Grade ≤ 1 with standard supportive therapy.
*Participants requiring a delay of ≥16 consecutive days should go off birinapant	
**Participants requiring > two dose reductions should go off birinapant.	
Recommended management: antiemetics.	

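### Sections 7.1.4, 6.5 and 7.1.2 disagree on whether return to a pre-existing baseline of grade 2 or higher counts as recovery after a birinapant-related grade 3 non-hematologic toxicity

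*Combined protocol and SAP*

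**What the plan says.** Section 7.1.4 governs birinapant-related non-hematologic toxicity. For a first or second grade 3 event the instruction is "Discontinue further birinapant or withhold birinapant until recovery to baseline or Grade" 1 or less, with restart at one dose level lower. For a second hold for grade 2, the same table has no baseline alternative: "hold until recovery to grade 1 and restart at one dose level lower".

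Section 6.5 is a stopping rule. It applies to any grade 3 toxicity that has not come back to at or below "grade 1 after 2 weeks of supportive care. The patient may continue with IMRRT but will be taken off birinapant". Section 7.1.2 repeats that rule. It adds a restart rule for a DLT related to the combination: birinapant and IMRRT are held for up to 2 weeks and, once the event is at or below "grade 1, treatment with birinapant will be resumed at 1 dose level lower".

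Two other provisions depend on these rules. The last DLT bullet in Section 6.2 counts toxicity of any grade that mandates stopping birinapant for more than 2 weeks. Section 6.1.1 makes a patient non-evaluable for DLT if less than 80% of planned birinapant and radiation was received within the 42 days.

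In Section 7.1.5.2 the grade 3 vomiting row reads "< Grade 1. Resume at same dose level". The grade 2 vomiting row, and the grade 3 rows for nausea (7.1.5.1) and diarrhea (7.1.5.3), all print grade 1 or less.

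**The concern.** Baseline and grade 1 or less are different targets when a patient enters with the toxicity already at grade 2 or higher. Such entries are plausible. All patients have had curative-intent radiotherapy or chemoradiotherapy (3.1.4), ECOG 2 is allowed (3.1.9), and Section 3 sets no general ceiling on residual non-laboratory toxicity.

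For such a patient, Section 7.1.4 permits a restart that Section 6.5 forbids, and sites could act differently on the same facts. At stake are that patient's remaining infusions and, in limited circumstances, whether the patient counts as a DLT or as evaluable in a cohort of 3 to 6.

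**Working it through.** The plan states no figure to reproduce. The check applies each rule to the same patient and then follows the result into the DLT and evaluability rules.

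**Step 1. Which patients meet the conflict**

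| Grade 3 event, birinapant-related | 7.1.4 | 6.5 and 7.1.2 stopping rule |
|---|---|---|
| Baseline grade 0-1, recovers to grade 1 | May restart one level lower | Not triggered |
| Baseline grade 2, returns to grade 2 and stays there | May restart one level lower | Off birinapant after 2 weeks |

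Only the second row conflicts. If the event is also a combination-related DLT, the 7.1.2 restart rule blocks the restart as well, because grade 1 is never reached.

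**Step 2. DLT counting (Section 6.2)**

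A grade 3 or higher non-hematologic event possibly attributable to the combination is already a DLT unless exempt, so the recovery rule does not change its count. For an exempt event, Section 6.5 makes stopping mandatory, which can bring it under the last DLT bullet; Section 7.1.4 does not make it mandatory. One such patient moves a cohort from 0 of 3 (escalate) to 1 of 3 (enter at least 3 more), or from 1 of 3 to 2 DLTs (stop).

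**Step 3. The 80% rule (Section 6.1.1)**

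Inputs: four infusions, on days 2 and 9 of two 21-day cycles, so study days 2, 9, 23 and 30; dose levels from Table 1. Assumption: planned dose is counted in mg/m², so a reduction counts against it.

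*Event on day 10, back to baseline grade 2 by day 23 and staying there.*

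- Under 7.1.4, infusions 3 and 4 are given one level lower:
  - level 3: (17+17+11+11)/(4×17) = 56/68 = 82%
  - level 4: (24+24+17+17)/(4×24) = 82/96 = 85%
- If infusion 3 is given but 6.5 then applies at 2 weeks (day 24), infusion 4 is lost:
  - level 3: (17+17+11)/68 = 45/68 = 66%
  - level 4: (24+24+17)/96 = 65/96 = 68%
- If the hold runs until grade 1 or less and the patient is then removed: 2/4 = 50% at either level.

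The patient passes 80% under 7.1.4 and fails under the other two readings. Levels 3 and 4 are the escalation cohorts remaining under the 12/15/2022 amendment.

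*Same timing at lower levels, under 7.1.4:* level 1 gives (5.6+5.6+2.8+2.8)/22.4 = 75%; level 2 gives (11+11+5.6+5.6)/44 = 75%. Both fail under any rule.

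*Reduction after infusion 1, none missed, under 7.1.4:* level 3 gives (17+3×11)/68 = 50/68 = 74%; level 4 gives (24+3×17)/96 = 75/96 = 78%. Both fail under any rule.

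Evaluability therefore changes in some sequences and not in others.

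**Step 4. Vomiting**

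A grade 3 episode that settles at grade 1 counts as recovered under 7.1.4 and 7.1.2. As printed, 7.1.5.2 keeps the hold, and the patient comes off birinapant only when the delay reaches 16 days.

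**The case against.** The strongest reply is that the rules can be obeyed together. The 7.1.4 grade 3 row allows outright discontinuation, so a site that stops under 6.5 breaks neither section. Section 6.5 is also a 2-week stopping test, not a restart test, and has not been triggered for a patient back at baseline within days. Both points are correct. They do not remove the conflict: a site that restarts as 7.1.4 permits still has a patient above grade 1 at 2 weeks, and 6.5 has no wording that treats the episode as closed at baseline.

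Several stronger readings are tempting, and the documents do not support them:

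- *Any recovered patient is affected.* The sections agree when baseline is grade 0-1. Section 7.1.4 covers birinapant-related events, so worsening attributed to radiation alone is outside its table.
- *The 7.1.4 remark on patients with toxicity at entry proves the point.* The words "if the study participant entered the study with existing toxicity" sit in the exception for asymptomatic grade 3 laboratory abnormalities resolving within 7 days. The conflict rests on the baseline wording in the grade 3 rule itself.
- *The vomiting rule is strictest for the middle grade.* Grade 4 vomiting stops birinapant by default, and re-initiation may be considered only for episodes under 24 hours. The printed sign for grade 3 may be a typing or text-extraction slip.
- *Losing one infusion always fails evaluability.* Three of four is 75%, below the 80% in 6.1.1, but 6.5 glosses its own 80% as fewer than 3 of 4 doses, and Section 9.2 calls a patient evaluable for toxicity after one dose.
- *The primary endpoint is generally at risk.* Non-exempt grade 3 events are DLTs already. The exemptions for nausea, vomiting and in-field effects themselves depend on the event being manageable over 2 weeks.

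**Conclusion.** The concern holds in a narrow form. For a birinapant-related grade 3 non-hematologic toxicity with a baseline of grade 2 or higher, 7.1.4 permits a restart that 6.5 and 7.1.2 rule out, and nothing gives precedence. Section 7.1.4 is not uniform either, since it drops the baseline alternative at the second grade 2 hold.

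The effect per affected patient is loss of the remaining infusions. DLT counting can change only for events otherwise exempt. Evaluability can change in some sequences: 82% against 66% or 50% at level 3, and 85% against 68% or 50% at level 4, if dose is counted in mg/m². The documents do not say how many patients enter with such a baseline, so no expected number or shift in the MTD can be calculated.

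The vomiting row is a secondary point to check; the main conflict stands without it.

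**What to change.** Reconcile Sections 6.5, 7.1.2 and 7.1.4, including the second grade 2 hold, so that they agree on whether return to a pre-existing baseline grade counts as recovery. Make clear how the reconciled rule relates to the Section 6.2 bullet on discontinuation for more than 2 weeks. Check the grade 3 vomiting threshold in 7.1.5.2 against its neighbouring rows, and either correct it or confirm that the difference is intended. Which recovery level applies is for the sponsor and investigators to decide.

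The cost is wording in a few places. No new data are needed, because Section 10.3.1 already provides a baseline form for adverse events before treatment.
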